9. ANALYSIS OF SAFETY

9.1 Deaths

Summary of all-cause mortality is provided in section 8.2.2.

9.2 Adverse Events

A summary of the percentage of patients who experience an early adverse event (≤ 30 day post-procedure) and late adverse event (>30 days post-procedure) will be reported for all adverse events.

 Edwards Lifesciences	Revision Date: January 22, 2019	Rev	 For Use Only by Affiliates of Edwards Lifesciences	Page 24 of 25
	Title	Statistical Analysis Plan for Edwards CLASP TR EFS		

When adverse event (AE) date is used to derive variables for analysis, missing dates will be imputed as follows:

- If the AE year is unknown, then no imputation will be performed.
- If the AE month is unknown, then
 - If the AE year matches the year of the index procedure/randomization*, then impute the month and day using the index procedure/randomization date.
 - Otherwise, assign "January".
- If the AE day is unknown, then:
 - If the AE month and year match the month and year of the index procedure/randomization, then impute the day using the index procedure/randomization date.
 - Otherwise, assign "01".

For study that all patients have intervention, use index procedure date. For study that some patients have intervention, some patients have medical therapy, use randomization date.

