## 11.2 AE Reporting Requirements

The Investigator will report all adverse events to the Sponsor as soon as possible, but no later than 10 working days after the Investigator first learns of the event.

Each adverse event must be reported on a separate AE CRF. In the event that the EDC system is not in service or otherwise not accessible, the Sponsor must be notified by email [REDACTED]. The AE CRF should be completed as soon as possible thereafter.

At the time of initial notification, the following minimal information must be provided:

- Study site number
- Patient ID number
- Site's awareness date
- AE description
- Causal relationship to device and implant procedure, if known

The site will provide the Sponsor copies of relevant supporting source documentation (e.g. admission H&P, implant procedure report, discharge summary, echocardiogram and laboratory results) for all adverse events requiring CEC adjudication (at a minimum, safety endpoints) and those events determined by the Sponsor to require additional investigation.

Adverse events must be followed until resolution, the patient is lost to follow-up, the patient has withdrawn consent, or the adverse event is otherwise explained.

The Investigator will inform their IRB and FDA of adverse events in accordance with the relevant local and regional regulatory requirements.

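### SAP 9.2 can count a late adverse event with a partial date as early, and gives events of unknown year no category

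*SAP*

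**What the plan says.** SAP 9.2 (Adverse Events) reports the percentage of patients with an "early adverse event (≤ 30 day post-procedure) and late adverse event (>30 days post-procedure"). Day 0 is the implant procedure date (SAP 5.1.1).

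The imputation rule follows: "When adverse event (AE) date is used to derive variables for analysis, missing dates will be imputed as follows". Its branches are:

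- Year unknown: "If the AE year is unknown, then no imputation will be performed".
- Month unknown, year equal to the procedure year: "then impute the month and day using the index procedure/randomization date".
- Month unknown, any other year: January.
- Day unknown, month and year equal to those of the procedure: "then impute the day using the index procedure/randomization date".
- Day unknown, any other month: the first of that month.

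The rule uses no other recorded date as a bound and specifies no sensitivity analysis. The trial does hold such dates. Protocol 8.16 (Table 11) schedules a safety evaluation at every visit, and Protocol 11.2 includes "Site's awareness date" in the minimum information for each initial AE notification.

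**The concern.** An earliest-date rule is a common default, but here the dates are then cut at day 30. Where the possible dates of an event lie on both sides of day 30, the rule decides its category without looking at the patient's record. An event first reported at the 1-year visit by a patient who attended the 30-day and 6-month visits without reporting it can be tabulated as occurring on the day of the procedure.

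The late percentage is the more exposed figure. This is a feasibility study with five years of follow-up, meant to guide later trials and device development (Protocol 4). Moving late events forward makes the late period look safer than it was. Separately, an event with no year has no stated place in either percentage, so a patient with a known event could be missing from both.

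**Working it through.** The plan states no figure on this point, so there is none to reproduce. The check applies the SAP 9.2 rule to every procedure date in 2019 and 2020 and every true event day from 0 to 1825 (the nominal 5-year visit, SAP 5.2). It compares the true category with the imputed one. Procedure dates and event days are assumed uniform. Counts below are for 2019; 2020 agrees to within 0.3 percentage points.

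**Direction.** The imputed day was never later than the true day, and no early event became late. Known-year errors therefore go only from late to early.

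**Month unknown, procedure year.** If R days of the year remain after the procedure, the possible true days are 0 to R. The late share is (R − 30)/(R + 1), or zero if R is 30 or less, and the rule sets all of them to day 0.

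- Procedure 1 July: R = 183, so 153/184 = 83% of possible days are late.
- Average over all procedure dates: 71%.
- Procedure 1 February 2019, event 20 December 2019: true day 322, imputed day 0.

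**Month unknown, following year.** January 1 is day 30 or less only for procedures on 2 to 31 December (30 of the 31 December dates). For December procedures, on average 96% of the days of the following year are truly late. Procedure 15 December 2019, event 20 November 2020: true day 341, imputed to 1 January 2020, day 17.

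**Day unknown, procedure month.** The true day is at most 30, so the event is early anyway and nothing is misclassified.

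**Day unknown, later month.** For 358 of 365 procedure dates (98%), the first of the next month is day 30 or less, so the event is forced to early. About 50% of the days in that next month are truly late. Procedure 5 March, event 28 April: true day 54, imputed day 27. No event later than true day 60 is affected. That extreme is a procedure on 30 January 2019 with an event on 31 March, imputed to 1 March, day 30.

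**Share of truly late events moved to early, if every such event had that kind of partial date:**

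| Missing part | True days 31–365 | True days 31–1825 |
|---|---|---|
| Month | 65,995 / 122,275 = 54% | 66,460 / 655,175 = 10% |
| Day only | 5,373 / 122,275 = 4.4% | 5,373 / 655,175 = 0.8% |

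The denominators are 365 procedure dates × 335 late days and 365 × 1,795 late days.

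**Weight of one patient.** SAP 2.2 plans 15 patients; Protocol 6 plans up to 65. (That difference is a separate matter; both serve here only as scale.) One patient is 1/15 = 6.7 points or 1/65 = 1.5 points. As an illustration with Clopper-Pearson intervals (SAP 6.1):

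- 3/15 = 20.0% (4.3 to 48.1) becomes 4/15 = 26.7% (7.8 to 55.1).
- 13/65 = 20.0% (11.1 to 31.8) becomes 14/65 = 21.5% (12.3 to 33.5).

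**Unknown year.** If such an event is left out of both categories, it can only lower the early or the late percentage. This is the one branch that can understate the early figure.

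**The case against.** The strongest reply is that little may depend on this. Partial dates may be few: Protocol 11.2 requires reporting within 10 working days of the investigator learning of an event, and safety is reviewed at each visit. The table is per patient, so a moved event matters only if it gives the patient a first early event or removes the only late one. The table is descriptive, is not a named endpoint, and is accompanied by a listing of all events. Known-year imputation is conservative for early safety. Event times that cluster soon after the procedure would make the late shares above smaller. All of this stands. It limits the size of the point but does not remove it: the rule as written can still contradict visit records, and the unknown-year gap remains.

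Three stronger readings are tempting and are not supported.

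- **That the early and late percentages are both wrong.** This would need partial dates that change a patient's status. Their number is not given.
- **That the 30-day MAE and clinical success are biased.** Both use CEC-adjudicated MAE data (SAP 8.1), and Protocol 11.2 has sites send source documents for adjudicated events. The SAP does not exempt MAE dates from the rule, so an effect can be neither shown nor excluded.
- **That the mention of randomization leaves the reference date unclear.** SAP 9.2 itself says that the procedure date applies where all patients have the intervention. The remaining words are template text with no analytic effect.

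Nor would an awareness or resolution date correct a known-year imputation. The imputed date is already the earliest possible, so an upper limit cannot move it. Only a later lower bound can.

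**Conclusion.** The point holds as a cheap improvement. SAP 9.2 can turn a truly late event into an early one in three situations: month unknown in the procedure year, month unknown in the next year after a procedure on 2 to 31 December, and day unknown in the month after the procedure (rarely, in March after a procedure at the end of January). The first is the material one.

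The early percentage can only be overstated, which is conservative. The late percentage can only be understated, which is anti-conservative. Unknown-year events are the exception, because their category is not stated.

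The total effect cannot be computed from the documents. It ranges from nothing, if all dates are complete or no patient's status changes, upward by at most 6.7 points (15 patients) or 1.5 points (65 patients) for each reclassified patient. The 71%, 83%, 96% and 50% late shares, and the 54% and 4.4% reclassified shares, rest on uniform timing and apply only to events with the stated kind of partial date.

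**What to change.** Amend SAP 9.2 as follows.

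1. Keep earliest-date imputation, but do not let the imputed date fall before the last attended visit at which the event had not been reported, where that fits the partial date. In the 1 February example, with a 6-month visit on day 180 and nothing reported, the date moves from day 0 to day 180 (31 July), which is late.
2. For unknown-year events, use that visit as the lower bound and the site awareness date as the upper bound.
3. If the remaining interval spans day 30, count the event as early in the main table, and also show the early and late percentages with it counted as late. This will still be needed: the 30-day visit may fall on days 23 to 37 (SAP 5.2), so a visit on or before day 30 does not settle the category.
4. State that MAE timing uses the CEC-adjudicated onset date where one is available. The sponsor should confirm that the committee records one.

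The cost is a short SAP revision and a little programming with visit and awareness dates that the trial already records. The downside is that the lower bound assumes an event would have been reported by the next attended visit. The two-way count should therefore also include events whose category depends on that assumption.

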12. APPENDIX

The Rev number has been changed [REDACTED] The footer was removed from the original document, but should have been there and no content changes have been made.
